4.4.2.3 Duration of Response

DOR is defined as the period measured from the date of the first occurrence of a CR or PR (whichever status is recorded first) until the first date that progressive disease or death is documented. Disease progression will be determined on the basis of investigator assessment with use of RECIST v1.1. DOR will be assessed in patients who have an objective response during the study as determined by the investigator with use of RECIST v1.1. Patients who have not progressed and who have not died by the date of data cutoff for analysis will be censored at the time of last tumor assessment date. Median DOR will be estimated using the Kaplan-Meier method, and the 95% CI will be calculated using the method of Brookmeyer and Crowley (1982). DOR analysis is performed on the basis of a non-randomized subset of patients (i.e., patients who achieve an objective response); therefore, formal hypothesis testing will not be performed for this endpoint. Comparisons between treatment arms will be made using the unstratified log-rank test for descriptive purposes only.

4.4.2.4 Patient-Reported Outcomes

Data from the EORTC QLQ-C30 questionnaire and two additional items from the EORTC Item Bank will be scored according to the EORTC scoring manual (Fayers et al. 2001).

The primary analysis population for evaluation of patient-reported outcome (PRO) assessments will include patients in a modified ITT population with a baseline PRO assessment and at least one post-baseline PRO assessment.

Data from the physical function scale and the global health status/quality of life sub-scale of the EORTC QLQ-C30 will be analyzed as time to clinically meaningful deterioration, which will be compared as secondary efficacy endpoints among treatment groups with use of the log rank test (2-sided). Confirmed clinically meaningful deterioration will be defined as a ≥ 10 -point decrease (on a transformed 0 to 100 score) from baseline on the physical function score or the global status/quality of life scores that must be held for at least two consecutive assessments or an initial ≥ 10 -point decrease from baseline followed by death within 4 weeks of the last assessment. Data for patients who do not achieve a 10-point decrease will be censored at the last time PRO data are available. The HR will be estimated using a stratified Cox proportional hazards model and its 95% CI will be provided.

Summary statistics (mean, standard deviation, median, and range) of absolute scores and mean changes from baseline will be calculated for all items and subscales of the EORTC QLQ-C30 and the two additional items from the EORTC Item Bank at each assessment timepoint for each arm while patients are receiving treatment. The mean (and 95% CI) and median of the absolute scores and the changes from baseline to each follow-up point will be reported for categorical and continuous variables, and the proportion of patients selecting each response option will be reported for the two additional items from the EORTC Item Bank. Previously published minimally important

differences (of 10 points) will be used to identify meaningful change from baseline within each treatment group on the functional and disease or treatment-related symptoms scales (Osoba et al. 1998; Cocks et al. 2011). Additional sensitivity analyses may be conducted.

A longitudinal analysis for the physical functioning and global health status/HRQoL subscales may be conducted to estimate the effect difference on PRO-repeated responses over a selected period of time and between the treatment arms, and mixed models on a set of covariates (baseline domain score, patient demographic, and clinical variables) may be conducted.

In the event of incomplete data, for all questionnaire subscales, if more than 50% of the constituent items are completed, a prorated score will be computed consistent with the scoring manuals and validation papers. For subscales with less than 50% of the items completed at a given timepoint, the subscale will be considered as missing. PRO completion, compliance rates, and reasons for missing data will be summarized at each timepoint by treatment arm.

Exploratory descriptive analyses will be conducted using post-treatment data.

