6.5 PATIENT-REPORTED OUTCOMES ANALYSES

For PROs, the EORTC QLQ-C30 questionnaire and two additional items will be scored according to the EORTC Scoring Manual.

The primary analysis population for evaluation of PRO assessments will include patients in the ITT population with a baseline PRO assessment and at least one post-baseline PRO assessment.

Data from the physical function scale and the global health status/quality of life will be analyzed as a time to deterioration, which will be compared as secondary efficacy endpoints among treatment groups with use of the log rank test (2-sided). Deterioration will be defined as 1) a decrease of 10 points on a transformed 0 to 100 score from baseline on the physical function score or the global status/quality of life scores, or 2) death, or 3) progression. The HR will be estimated using a stratified Cox proportional hazards model and its 95% CI will be provided.

For each assessment timepoint and for each treatment arm, the mean (and 95% CI) and median (and inter-quartile ranges) of the absolute scores for the EORTC QLQ-C30 and additional items and their changes from baseline (Cycle 1 Day 1), will be calculated.

Exploratory descriptive analyses will be conducted using post-treatment data.

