Stratification factors are extended RAS mutation status of the tumor and time since diagnosis of first metastasis (< 18 months vs. ≥ 18 months). Permuted-block randomization will be applied to ensure a balanced assignment to each treatment arm. Randomization and stratification will be managed through an interactive voice/web response system (IxRS).

At least 50% of patients with extended RAS-mutant tumors (refer to Protocol Section 4.5.7.1 for definition) will be enrolled in each arm. Enrollment of patients with microsatellite (MSI)-high status (see Protocol Section 4.5.7.1 for definition) will be limited to approximately 5% to reflect the natural prevalence in mCRC ([Goldstein et al. 2014](#)). [Figure 1](#) illustrates the study schema.

Figure 1 Study Schema

Stratified by tumor extended RAS status and time since diagnosis of first metastasis
MSI-H capped at approximately 5%
At least 180 patients with extended RAS-mutant tumors to be enrolled

mCRC=metastatic colorectal cancer; MSI-H=microsatellite high.

Patients will undergo tumor assessments at baseline and every 8 weeks (± 7 days), regardless of any dose delays or treatment cycle, until documented investigator-determined progressive disease, loss of clinical benefit, withdrawal of consent, death, or study termination by the Sponsor, whichever occurs first. Tumor response will be evaluated according to Response Evaluation Criteria in Solid Tumors Version 1.1 (RECIST v1.1). Any evaluable and measurable disease must be documented at screening and re-assessed at each subsequent tumor evaluation.

Treatment will continue until the patient has disease progression according to RECIST v1.1, unacceptable toxicity, death, patient or physician decision to withdraw, or pregnancy, whichever occurs first. Patients in all treatment arms are allowed to receive study treatment beyond disease progression if certain conditions are met (see Protocol Section 4.3.2.4).

After completion of study treatment, patients may receive any subsequent line of therapy as directed by their treating physician.

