4.4.1 Primary Efficacy Endpoint

The primary efficacy endpoint is OS. Overall survival is defined as the time between the date of randomization and the date of death due to any cause. Data for patients who are not reported as having died at the time of analysis will be censored at the date they were last known to be alive. Data for patients who do not have post-baseline information will be censored at the date of randomization plus 1 day.

Comparisons with respect to OS for each of the two comparisons between treatment arms will be tested based on a stratified log-rank test in the ITT populations in the analysis at the two-sided level of significance as described in Section 2.3. The stratification factors will be those used for randomization (i.e., extended RAS

mutation status (yes vs. no) and time since diagnosis of first metastasis [< 18 months vs. ≥ 18 months]), and will be obtained from the IxRS.

The null and alternative hypotheses can be phrased in terms of the survival functions $S_E(t)$ and $S_C(t)$, where $S_E(t)$ represents the survival function for experimental arm (either Arm A or Arm B) and $S_C(t)$ represents the survival function for Arm C:

$$H_0: S_E(t) = S_C(t) \text{ versus } H_1: S_E(t) \neq S_C(t)$$

The HR (λ_E/λ_C , where λ_E represents the hazard of death in experimental arm [either Arm A or Arm B] and λ_C represents the hazard of death in Arm C, comparing the treatment effect between the two treatment arms) will be estimated using a stratified Cox regression model with the same stratification variables used for the stratified log-rank test, and the 95% CI will be provided. Results from an unstratified analysis will also be provided.

Kaplan-Meier methodology will be used to estimate median OS and to construct survival curves for each treatment arm for a visual description of the difference among arms. The Brookmeyer-Crowley methodology will be used to construct the 95% CI for the median OS ([Brookmeyer and Crowley 1982](#)).

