4.4.2 Secondary Efficacy Endpoints

4.4.2.1 Progression-Free Survival

PFS is defined as the time between the date of randomization and the date of first documented disease progression or death, whichever occurs first. Disease progression will be determined on the basis of investigator assessment using RECIST v1.1. Data for patients who are alive and have not experienced disease progression at the time of analysis will be censored at the date of last tumor assessment. Data from patients with no post-baseline tumor assessment will be censored at the randomization date plus 1 day. PFS will be analyzed using the same methods as described in Section 4.4.1.

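### PRO time to deterioration: the log-rank test is not specified as stratified or as pairwise, although the hazard ratio reported beside it is stratified

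*SAP*

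**What the plan says.** **PRO endpoints.** SAP 4.4.2.4 analyses physical function and global health status/quality of life as time to deterioration, compared "among treatment groups with use of the log rank test (2-sided". For the estimate it says "The HR will be estimated using a stratified Cox proportional hazards model and its 95% CI will be provided". It does not name the strata. Protocol 6.5 likewise compares the arms "with use of the log rank test (2-sided" and also takes the hazard ratio from a stratified Cox model.

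**Other endpoints in the SAP.**
- OS (4.4.1) is "tested based on a stratified log-rank test in the ITT populations", and its Cox model is fitted "with the same stratification variables used for the stratified log-rank test". The strata come from the IxRS.
- PFS (4.4.2.1): "PFS will be analyzed using the same methods as described in Section 4.4.1".
- ORR (4.4.2.2) uses a stratified Cochran-Mantel-Haenszel test.
- DOR (4.4.2.3): "Comparisons between treatment arms will be made using the unstratified log-rank test for descriptive purposes only".

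**Design.** SAP Section 2: "Stratification factors are extended RAS mutation status of the tumor and time since diagnosis of first metastasis". With two levels each, this makes four strata. The SAP amendment rationale and Section 2.3 confine the testing hierarchy to the two OS comparisons.

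**The concern.** PRO deterioration is the one formally compared time-to-event endpoint whose test carries no stratification label while its hazard ratio does. Taken at its word, a log-rank test with no strata pools all patients in one risk set. The p-value then comes from a pooled analysis and the confidence interval from a stratified one. A report could show p above 0.05 beside an interval that excludes 1, or the reverse. If the strata predict deterioration, the pooled test also gives up some power.

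If the wording is instead read as leaving the choice open, the test for two secondary efficacy endpoints can be settled at analysis in an open-label trial.

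There is a second gap. The phrase about treatment groups does not say whether the test is pairwise against Arm C or one test across three arms. A three-arm test on 2 degrees of freedom would match no pairwise hazard ratio.

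**Working it through.** **1. The plan's own figures.** No power, effect size or event count is given for the PRO endpoints. The only stated power is for OS (SAP 2.3 and Table 1), and it reproduces. Power = Φ(|ln HR| × √(d × p × (1 − p)) − 1.96), with d events and p the experimental share.
- A vs C: d = 178, p = 2/3, HR 0.61. 0.494 × √39.56 − 1.96 = 1.15, so 87.5% (stated 87%).
- B vs C: d = 127, p = 1/2. 0.494 × √31.75 − 1.96 = 0.83, so 79.5% (stated 80%).
- Minimum detectable HR = exp(−1.96/√(d × p × (1 − p))): 0.732 and 0.706 (stated 0.73 and 0.71).

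None of these figures depends on the PRO wording.

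**2. Simulating the two readings.** Both tests were run on the same simulated data. The statistic is z = Σ(g − q)/√Σ q(1 − q), summed over events. Here g is 1 for an event in the experimental arm and 0 otherwise, and q is the experimental share of those at risk. The unstratified test forms the risk set from all patients; the stratified test forms it within each of four strata. Significance is |z| > 1.96.

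From the documents: arm sizes of about 180, 90 and 90, four strata, two-sided 0.05. Assumed: exponential times, control median 4 months, uniform censoring over 0 to 20 months, equal strata balanced across arms, treatment HR 0.65 (or 1.0 for type I error), and each stratification factor carrying a hazard ratio of 1.0, 1.3, 1.5 or 2.0. There were 6,000 trials per scenario.

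| Comparison | Per-factor HR | Power, unstratified | Power, stratified | Gain from stratifying (points) | Tests disagree | Type I error, unstratified / stratified |
|---|---|---|---|---|---|---|
| A vs C | 1.0 | 77.4% | 76.2% | −1.2 | 4.3% | 5.1% / 5.2% |
| A vs C | 1.3 | 77.1% | 77.4% | +0.3 | 4.9% | 5.0% / 5.0% |
| A vs C | 1.5 | 73.6% | 76.8% | +3.2 | 6.7% | 4.4% / 5.0% |
| A vs C | 2.0 | 66.8% | 75.8% | +9.0 | 11.9% | 3.6% / 5.4% |
| B vs C | 1.0 | 64.2% | 62.7% | −1.5 | 6.2% | 5.2% / 5.3% |
| B vs C | 1.3 | 61.8% | 61.4% | −0.4 | 7.1% | 5.3% / 5.4% |
| B vs C | 1.5 | 61.0% | 63.3% | +2.3 | 8.6% | 4.7% / 5.3% |
| B vs C | 2.0 | 54.5% | 62.1% | +7.6 | 12.6% | 3.6% / 5.6% |

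The disagreement column is at treatment HR 0.65.

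**3. Simulation error.** For a paired difference Δ with disagreement rate D, the standard error is √((D − Δ²)/6000). For A vs C at 1.3 this is √((0.049 − 0.003²)/6000) = 0.3 points, so that difference cannot be told from zero. For B vs C at 1.5 it is √((0.086 − 0.023²)/6000) = 0.4 points, so a gain of 2.3 is real under these assumptions.

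**4. Reading the table.** Disagreement does not need prognostic strata: it is already 4% to 6% when the factors carry no effect. The stratified log-rank is the score test of the stratified Cox model, so its result is a close stand-in for whether the Cox interval excludes 1, not an exact one. The power levels are not forecasts, since the PRO population is smaller than the randomised arms; the contrast between the two tests is the useful part.

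**The case against.** A reader might infer that the plan deliberately chose an unstratified test. The documents do not support that. The SAP writes unstratified where it means it, for DOR and for the supplementary OS analysis, and the PRO text has no such word. An omitted adjective is at least as plausible, given the stratified Cox model in the same paragraph. This stands: the defect is an unspecified test whose literal reading conflicts with its estimate.

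A reader might also infer that power is certainly lost. That is conditional too. Protocol 3.3.3 describes the factors as prognostic, but for survival. Under SAP 4.4.2.4 progression is not an event, and death counts only shortly after an initial 10-point fall, so prognosis for survival cannot simply be carried over. Protocol 6.5 does count death and progression, which makes some effect plausible there, but the SAP governs for filing. With weak strata the loss is nil or slightly negative, and no planned PRO power exists to be undermined.

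Finally, no alpha-controlled claim rests on a PRO p-value, and disagreement matters only near 0.05. This also stands and limits the weight of the point. It does not remove the mismatch, since the SAP says that secondary analyses will be submitted to health authorities.

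**Conclusion.** The point holds as a minor one, a free improvement. Both documents leave the PRO log-rank without strata and without named pairs, beside a stratified hazard ratio. Run literally, p-value and interval come from different analyses. They would disagree in about 4% to 13% of trials at an assumed treatment HR of 0.65.

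The literal test is not invalid. Its simulated type I error is 3.6% to 5.3%, so any departure is towards conservatism, and an inference that false positives are inflated would be wrong. The power cost runs from about nil at a per-factor HR of 1.3 to 8 to 9 points at 2.0; with no prognostic effect, stratifying costs about 1 to 1.5 points. Those factor strengths, the treatment effect and the event-time model are assumptions. The textual mismatch is certain; the size of the power effect is not.

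**What to change.** In SAP 4.4.2.4 and Protocol 6.5, specify a two-sided log-rank test stratified by extended RAS status and time since diagnosis of first metastasis, using the IxRS values. State that it is applied pairwise, Arm A vs Arm C and Arm B vs Arm C. Name the same strata for the Cox model, as SAP 4.4.1 does for OS. An unstratified result may be added as supportive, as is planned for OS.

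The cost is a short wording change in each document. It needs no extra data or patients and leaves the OS hierarchy and sample size as they are. The only statistical price is about 1 to 1.5 points of power if the strata turn out to have no bearing on deterioration.

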4.5.10 Patient-Reported Outcomes

PRO data will be collected via the EORTC QLQ-C30 and two additional items from the EORTC item bank (see Section 4.5.10.1) to more fully characterize the clinical profile of cobimetinib plus atezolizumab as compared to regorafenib. In addition, to derive utility for pharmacoeconomic models, patients will complete the EQ-5D-5L.

The questionnaires will be translated as required in the local language. To ensure instrument validity and that data standards meet health authority requirements, questionnaires scheduled for administration during a clinic visit will be completed in their entirety by the patient prior to the performance of non-PRO assessments and the administration of study treatment (where applicable).

Patients will use an electronic PRO (ePRO) device to capture PRO data at in-person clinic visits. The ePRO device and/or instructions for completing the PRO questionnaires electronically will be provided by the investigator staff. The data will be transmitted via a pre-specified transmission method (e.g., web or wireless) automatically after entry to a centralized database at the ePRO vendor. The data can be accessed by the appropriate sponsor study personnel securely via the Internet.

The questionnaires will be completed on the ePRO tablet at the beginning of each cycle upon arrival at the study clinic during treatment period and at the treatment discontinuation visit. The assessments should continue until loss of clinical benefit and then follow the survival follow-up frequency at 3 and 6 months. If the survival follow-up study visits are conducted by telephone, the PRO data (the reduced EORTC QLC 30) for that visit will be collected via telephone interview and recorded by the investigative staff on the ePRO tablet.

Adverse event reports will not be derived from PRO data by the Sponsor.

4.5.10.1 European Organization for Research and Treatment of Cancer Quality of Life-C30 Questionnaire and Additional Items

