- ^s PRO instruments EORTC QLQ-C30 and EQ-5D-5L will be completed in this order using an electronic device on Day 1 of each cycle during a visit and prior to any assessments. Data will be collected at end of study and at survival follow-up at 3 and 6 months only. In the event a study visit is conducted by telephone, the PRO data for that visit will be collected via telephone interview and recorded by the investigative staff on the ePRO tablet. To maintain validity and minimize patient burden, the PRO instruments administered via telephone interview will consist of a reduced version of the EORTC QLQ items (Items 1–7, 10, 12, 13, 16, 17, 18, 29, and 30 from the C30 and the two additional items from the item bank) and the telephone interview version of the EQ-5D-5L.
- ^t The initial dose will be delivered over 60 (\pm 10) minutes. If the first infusion is well tolerated all subsequent infusions will be delivered over 30 (\pm 10) minutes until loss of clinical benefit. *Dose can be given \pm 7 days from scheduled Day 1 of each cycle.*
- ^u Cobimetinib 60 mg/day PO will be given in a 21/7 dosing schedule. *Dose can be given \pm 7 days from scheduled Day 1 of each cycle, but the scheduled 7-day break must be \geq 5 days.*

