- ^o All serious adverse events and Adverse Events of Special Interest, regardless of relationship to study drug, will be reported until 90 days after the last dose of study drug or initiation of new anti-cancer therapy, whichever occurs first. All other adverse events, regardless of relationship to study drug, will be reported until 30 days after the last dose of study drug or initiation of new anti-cancer therapy, whichever occurs first. After this period the investigator should report any serious adverse events or adverse events of special interest that are believed to be related to prior study drug.
- ^p Archival or fresh baseline tumor tissue collected during screening; Optional on treatment biopsy at Cycle 1 Day 15 ± 5 days; Mandatory biopsy at progression if clinically feasible.
- ^q PRO instruments EORTC QLQ-C30 and EQ-5D-5L will be completed in this order using an electronic device on Day 1 of each cycle during a visit and prior to any assessments. Data will be collected at end of study treatment and at survival follow-up at 3 and 6 months only. In the event a study visit is conducted by telephone, the PRO data for that visit will be collected via telephone interview and recorded by the investigative staff on the ePRO tablet. To maintain validity and minimize patient burden, the PRO instruments administered via telephone interview will consist of a reduced version of the EORTC QLQ (Items 1–7, 10, 12, 13, 16, 17, 18, 29, and 30 from the C30 and the two additional items from the item bank) and the telephone interview version of the EQ-5D-5L.
- ^r Patients who discontinue treatment for reasons other than disease progression (e.g., toxicity) will continue scheduled tumor assessments until disease progression, withdrawal of consent, study termination by Sponsor, or death, whichever occurs first.

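### The SAP's 4-week death limb stops short of the 3-month questionnaire that follows treatment discontinuation, so some patients who deteriorate and then die are not counted as deteriorated

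*SAP*

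**What the plan says.** SAP 4.4.2.4 analyses physical function and global health status as time to deterioration, compared by log-rank test with a stratified Cox HR. The two scales are secondary efficacy endpoints. A fall of at least 10 points becomes an event by one of two limbs. The first asks for confirmation, that is, a fall "that must be held for at least two consecutive assessments". The second lets an early death stand in for confirmation: "or an initial ≥ 10 -point decrease from baseline followed by death within 4 weeks of the last assessment". Censoring is covered by one sentence: "Data for patients who do not achieve a 10-point decrease will be censored at the last time PRO data are available". The section ends: "Exploratory descriptive analyses will be conducted using post-treatment data".

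The questionnaire schedule is in Protocol 4.5.10 and the schedules of assessments. Questionnaires are due "at the beginning of each cycle upon arrival at the study clinic during treatment period and at the treatment discontinuation visit". After that, "The assessments should continue until loss of clinical benefit and then follow the survival follow-up frequency at 3 and 6 months". The SAP Appendix 2 footnote for Arm A reads "Data will be collected at end of study and at survival follow-up at 3 and 6 months only"; for Arms B and C it reads "Data will be collected at end of study treatment and at survival follow-up at 3 and 6 months only". Protocol 4.5.11.3 places the discontinuation visit within 30 days of the last dose and lets the visit at which loss of clinical benefit is determined serve as that visit.

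Protocol 6.5 defines deterioration differently: a 10-point fall, or death, or progression. SAP section 4 says that the SAP supersedes the protocol for a regulatory filing.

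**The concern.** The 4-week limb is there to rescue a fall that death prevented from being confirmed. On treatment it roughly matches the 21- or 28-day cycle. After discontinuation it does not, because the next chance to confirm is about 3 months away. A patient who first reports a fall at the discontinuation visit and dies between those two points is a non-event, although no questionnaire was missed and the only score after the fall began showed deterioration.

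Two gaps in the text make this worse. The censoring sentence is written for patients who never had a 10-point fall, so taken literally it does not reach this patient. And if the closing sentence on post-treatment data means those data are descriptive only, a fall first seen at discontinuation can never be confirmed, whatever the patient's survival.

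At stake is informative censoring. The patients dropped as events are failing and close to death, and there are proportionately more of them in an arm with shorter survival. In an open-label trial, the handling of these patients should not be left to programming.

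**Working it through.** The plan gives no event count, power or sample size for this endpoint, so there is no figure of its own to reproduce. The check sets the rule against the schedule and then sizes the gap.

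**Rule against schedule, for a first fall at the discontinuation visit**

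| What happens next | Two consecutive falls? | Death within 4 weeks? | Event? |
|---|---|---|---|
| Dies by week 4 | No | Yes | Yes |
| Dies after week 4, before the 3-month questionnaire | No | No | **No** |
| Completes the 3-month questionnaire, fall still present | Yes, if that questionnaire counts | Not needed | Yes, if it counts |

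A fall already present at the preceding cycle visit and still present at discontinuation is confirmed there, so it is unaffected.

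**Share of such patients who die in the uncovered window**

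Inputs: planning median OS of 6.4 months (Arm C) and 10.5 months (Arms A and B), from SAP 2.3. Assumptions: exponential survival, and these medians applied from the discontinuation visit. The documents give no survival after discontinuation, so a 4-month median is added as an assumed shorter case.

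With λ = ln 2 / median and 4 weeks = 0.920 months:

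P = exp(−0.920λ) − exp(−3λ)

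If month 3 instead runs from the last dose and the discontinuation visit is on day 30, the upper limit becomes 3 − 30/30.44 = 2.014 months after that visit.

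| Median (months) | λ | Alive at 4 weeks | Alive at 3 months | P, month 3 from discontinuation | Alive at 2.014 months | P, month 3 from last dose |
|---|---|---|---|---|---|---|
| 6.4 | 0.1083 | 0.9052 | 0.7226 | 18.3% | 0.8040 | 10.1% |
| 10.5 | 0.0660 | 0.9411 | 0.8203 | 12.1% | 0.8755 | 6.6% |
| 4 (assumed) | 0.1733 | 0.8527 | 0.5946 | 25.8% | 0.7054 | 14.7% |

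For month 3 counted from discontinuation, assumed medians of 5, 3 and 2 months give 22%, 31% and 37%.

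**Effect on the HR**

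Suppose a fraction f of deterioration events in each arm are first falls at discontinuation, and the uncovered ones are dropped and censored. Each arm's event hazard is then scaled by the share retained, so the HR is multiplied by about (1 − 0.121f) / (1 − 0.183f):

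- f = 1: 0.879 / 0.817 = 1.08
- f = 0.5: 0.9395 / 0.9085 = 1.03
- f = 0.3: 0.9637 / 0.9451 = 1.02

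With the shorter window and f = 1 it is 0.934 / 0.899 = 1.04. Borrowing the OS design HR of 0.61 for scale, the most extreme of these cases moves it to 0.61 × 1.08 = 0.66.

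**On treatment**

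In Arms A and C the next visit is at day 28 with a ±3-day window, so deaths on days 29-31 could be missed. At a 6.4-month median, the chance of death in 3 days is 1 − exp(−0.1083 × 3/30.44) = 1.1%, and it applies only to a patient with an unconfirmed fall and a late visit.

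**The case against.** The best case against raising this is that the gap affects a subset of unknown size, that the percentages borrow OS medians measured from randomisation, and that how near death must be to stand in for confirmation is a design preference. The first two stand: the figures are illustrations. The third stands in part. A fixed window is defensible, but not one that ends about two months before the next chance to confirm.

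A second objection is that the censoring sentence follows directly on the definition of confirmed deterioration, so it can be read as covering everyone who does not meet that definition. That is a sensible reading, but it is not what the sentence says, and the ambiguity costs one line to remove. Nor does it answer the main point, since the patient would still be a non-event.

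Protocol 4.5.10 might suggest that questionnaires go on until loss of clinical benefit in a patient who stops for toxicity. No schedule table contains such a visit between discontinuation and month 3.

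A reader might also infer that the rule misfits on treatment, because the cycles differ by arm. The effect there is about 1% in a small subset. Tying the on-treatment window to the next visit would make the event definition differ by arm (about 24 days in Arm B, 31 in Arms A and C), which the common 4-week limb avoids.

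**Conclusion.** The gap is real. Under the SAP, a patient whose first 10-point fall is at discontinuation and who dies after week 4 but before the 3-month questionnaire is not counted as deteriorated, and no sentence says clearly how that patient is handled. If post-treatment questionnaires are descriptive only, the gap is wider.

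At the planning medians, 12-18% of such patients fall in the gap, or 7-10% with month 3 counted from the last dose; shorter residual survival gives more. These are shares of patients with a first fall at discontinuation, not of all patients or all events.

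A reader might infer that the rule could carry the HR past no difference. The documents do not support that. Even if every event were of this kind, the factor is about 1.08, so the true HR would have to be about 0.93 (1/1.08) or higher already. The direction, towards no difference, also assumes that first falls at discontinuation make up a similar share of events in each arm.

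Priority is low: the SAP's testing hierarchy contains only the two OS comparisons, so no confirmatory claim rests on these endpoints.

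**What to change.** In SAP 4.4.2.4:

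- Keep the common 4-week death limb on treatment, for all arms.
- For a first fall at the treatment discontinuation visit, count death before the 3-month follow-up questionnaire, plus its window, as deterioration. State that window and whether month 3 runs from the last dose or from the discontinuation visit.
- State that the discontinuation, 3-month and 6-month questionnaires count for confirmation, so that the sentence on post-treatment data cannot be read to exclude them.
- Censor any other unconfirmed fall at the last available PRO assessment.
- Run the Protocol 6.5 definition, with death and progression as events, as a sensitivity analysis, and acknowledge that the two documents differ.

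The cost is SAP wording and programming, with no new data. The downside is that some deaths up to about 3 months after a single unconfirmed fall will count as deterioration. That moves towards the protocol definition, which already counts death as an event.
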